#### 14.3.1. Planned Interim Analysis

There is no planned formal interim statistical analysis of treatment effectiveness. However, an integral internal pilot phase will allow a feasibility assessment, examining recruitment, and retention. As part of continuous oversight, the DMC will be provided with confidential reports by trial arm, containing information on recruitment, protocol compliance, safety, and interim

assessments of outcomes (between-group estimates of differences in efficacy and/or safety outcomes), as agreed.

#### 14.4. Funder Feasibility Assessment

The funder feasibility assessment will take place 8 months after the planned start of recruitment (trial month 19). Site opening, recruitment, treatment adherence, diary completion and primary outcome completion will be assessed at this timepoint. Thresholds for the individual categories are outlined below.

**Table 11 - Progression criteria**

Progression criteria	Green – proceed	Amber – improve	Red – stop (Following discussions with TSC and Funder)
Site Opening	≥17 sites open to recruitment	12-16 sites open to recruitment	≤11 sites open to recruitment
Participant recruitment	≥248 participants recruited (≥100%)	186-247 participants recruited (75- <100%)	≤185 participants recruited (<75%)
Treatment adherence (Percentage of randomised participants reaching satisfactory adherence level)	≥100% of randomised participants	75- <100% of randomised participants	<75% of randomised participants
Bleeding diary adequate completion (Percentage of randomised participants adequately completing the diary)	≥100% of randomised participants	75- <100% of randomised participants	<75% of randomised participants
Perception of bleeding pattern questionnaire completed at 90 days (primary outcome)	100% of randomised participants who have reached 90 days follow-up	75- <100% of randomised participants who have reached 90 days follow-up	<75% of randomised participants who have reached 90 days follow-up

At trial month 19, when the Funder assessment is undertaken, if the trial progress falls into the green category then the trial will continue to recruit without adjustment. If the trial is assessed as amber, a recovery strategy would be implemented with the support of the trial oversight committees (TMG, DMC and TSC). If the trial is assessed as red, a recovery strategy or closure plan would need to be implemented, following consultation with oversight committee members and Funder input. If there is inconsistency in the scoring of the progression criteria then overall the trial will be categorised according to the criterion that is furthest from achieving the progression threshold (e.g. if two criteria are green but one is amber, the trial will be categorised as amber).

The progress of the trial will be continually monitored by the trial team and Funder. Recruitment and trial procedures will continue during the decision-making process.

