### 14. Statistical Considerations

#### 14.1. Sample size calculation

We have powered the trial to establish the non-inferiority of desogestrel compared to the COCP in settling problem bleeding. Data from previous studies [10, 23] show that approximately 90% of implant users would experience significant improvement in bleeding pattern with COCP or ulipristal treatment within the 90 days reference period. To be conservative we have used a reference group proportion of 85%. There are no validated minimum clinically important differences for improvement in bleeding pattern, but our sexual health clinical experts and patient representatives advised that, due to its advantages, adoption of desogestrel would be recommended even if it has a slightly less improvement rate in bleeding pattern of at least 75%. This represents an absolute non-inferiority margin of 10% and was judged to be a clinically relevant margin. A sample size of 276 per arm (552 total) would be required to achieve 90% power to detect non-inferiority of desogestrel compared to COCP within a non-inferiority margin of 10% based on one-sided 2.5% significance level, 1:1 allocation, and a likelihood score test statistic (Farrington and Manning) assuming the actual between-group difference in improvement proportion is zero. Allowing for up to 20% missing primary outcome data, we plan to randomise 690 participants.

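### Table 11 sets green at 100% on three participant-level rows, against a sample size that allows 20% missing outcomes; two of these rows also lack a follow-up limit

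*Protocol*

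**What the plan says.** Section 14.4 of the protocol places the funder feasibility assessment 8 months after the planned start of recruitment (trial month 19). Table 11 has five criteria:

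- **Sites and recruitment.** Green is 17 or more sites and 248 or more participants. The recruitment percentages are percentages of the target of 248.
- **Treatment adherence**, described as "Percentage of randomised participants reaching satisfactory adherence level", and **diary completion.** Green is written as at least 100% of randomised participants, amber as 75% to below 100%, red as below 75%. No minimum follow-up is stated.
- **Day-90 primary-outcome questionnaire.** Green is "100% of randomised participants who have reached 90 days follow-up". Amber and red use the same 75% cut and the same restriction to participants at day 90.

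If the rows disagree, "overall the trial will be categorised according to the criterion that is furthest from achieving the progression threshold". Amber leads to a recovery strategy supported by the TMG, DMC and TSC. Red leads to a recovery strategy or a closure plan after consultation.

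Section 14.1 states: "Allowing for up to 20% missing primary outcome data, we plan to randomise 690 participants".

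**The concern.** Green should describe a trial that is going as planned. Here it describes one with no missing primary outcome, no participant below the adherence standard and no inadequate diary. The protocol's own rules make such losses likely. Table 8 withdraws anyone whose implant is removed and asks for no further questionnaires or diaries. It also lets participants leave treatment, diary or questionnaires separately. If these people stay in the denominator, as the wording reads, one of them rules out green.

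Because the worst row decides, a trial at or above its planning assumption would be sent into a recovery strategy. It would share a rating with one at 75% to 80%, which is below plan.

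The denominators also differ within the table. Participants recruited shortly before the assessment cannot have a full course of pills or diary, yet they count in the adherence and diary rows.

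**Working it through.** **1. The 80% planning value.** Inputs from section 14.1: 85% in both arms, margin 10 points, one-sided 2.5%, 90% power, Farrington-Manning score test. The restricted estimates under the null are 0.787 and 0.887.

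- s0 = √(0.7874×0.2126 + 0.8874×0.1126) = 0.517
- s1 = √(2×0.85×0.15) = 0.505
- n = (1.960×0.517 + 1.282×0.505)² / 0.10² = 275.7, so 276 per arm and 552 in total
- 552 / 0.80 = 690

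The plan's figures are reproduced, and 690 rests on 80% completeness. The recruitment row is also consistent: 0.75 × 248 = 186.

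**2. How many have reached day 90 at month 8.** The protocol gives 248 by month 8 and, in section 3.2, 690 over 17 months. It gives no accrual shape, so three are assumed. A month is 30.4375 days, so the day-90 cut-off falls at 8 − 90/30.4375 = 5.04 months.

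- *Uniform to month 8:* 5.04/8 = 63%, or 156 people.
- *Linear ramp, then constant, fitted to both totals:* 9λ = 690 − 248, so λ = 49.1 per month; half the ramp is 8 − 248/49.1 = 2.95 months, so the ramp lasts 5.9 months. The number at day 90 is 49.1 × 5.04² / (2×5.9) = 106, or 43%.
- *Quadratic to month 8:* (5.04/8)² = 40%, or 99 people.

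Constant accrual throughout would give 690 × 8/17 = 325 by month 8, so a target of 248 implies some ramp-up.

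**3. Chance of green in the primary-outcome row.** With true completion p and n people at day 90, assumed independent, this is pⁿ.

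| True completion | n = 156 | n = 106 | n = 99 |
|---|---|---|---|
| 80% | 8×10⁻¹⁶ | 5×10⁻¹¹ | 3×10⁻¹⁰ |
| 95% | 0.0003 | 0.004 | 0.006 |
| 98% | 0.04 | 0.12 | 0.14 |
| 99% | 0.21 | 0.35 | 0.37 |

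For a row counted on all 248 participants, the chance is 3×10⁻⁶ at 95% and 0.08 at 99%. Overall green needs all three rows at 100% together, so it cannot be more likely than the least likely row.

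**4. Chance of red in the primary-outcome row at a true 80%.** The binomial probability of falling below 75% is 5% (n = 156), 10% (n = 106) or 12% (n = 99).

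**5. Timing in the adherence and diary rows.** Suppose a participant must have accrued d days to count as satisfactory and all 248 are in the denominator. The highest percentage attainable is then:

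| Days required | Uniform | Fitted ramp | Quadratic |
|---|---|---|---|
| 36 | 85% | 77% | 73% |
| 63 | 74% | 59% | 55% |
| 90 | 63% | 43% | 40% |

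The values 36 and 63 are category limits in Table 10, which grades adherence out of 90 pills and classes fewer than 36 as non-adherence. With 63 or 90 days required, every shape lies below 75%. With 36 days, only the quadratic shape does; under the fitted ramp, 0.75/0.766 = 98% of those with enough follow-up would have to be adherent to avoid red. If scoring is relative to days elapsed, the ceiling is 100%.

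**6. Timing in the primary-outcome row.** The restriction to day 90 removes this problem. What remains is that people at days 90 to 100 may still be inside the 10-day questionnaire window (section 8.2.11).

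**The case against.** Four points can be made for the table, and a reader might infer more than it supports.

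- **The 20% is a tolerance, not a target.** This is fair: section 14.1 says up to 20%, and the team may expect better. But the row fails to return green even at 95%, and usually at 98%.
- **Red forced by timing.** A reader might infer that month 8 must produce red. The documents do not support that. The primary-outcome row excludes people not yet at day 90. For the other two rows, Table 11 does not define *satisfactory* or *adequately*; pills and bleeding are recorded daily and could be scored pro rata; and sections 14.3 and 14.4.5 leave the compliance cut-off to the SAP. At the one non-adherence cut-off in the protocol, 36 pills, the fitted ramp leaves the ceiling at 77%, just above red. The quadratic shape, which goes below, fits poorly: it ends at 2×248/8 = 62 per month, and 248 + 9×62 = 806 by month 17, not 690, unless accrual then slows. What stands is that the wording allows the problem in two rows.
- **An automatic stop, or the only stop/go rule.** Neither is supported. Red leads to discussion and a recovery or closure plan, and recruitment continues meanwhile. The DMC and TSC can also act under sections 16.4 and 16.5.
- **The table still discriminates.** Partly true. The site and recruitment rows work normally, and a red line at 75% lies sensibly just below the 80% assumption. The defect is at the green end.

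**Conclusion.** The green thresholds are wrong as written. On the protocol's own 80% completeness, the primary-outcome row has a chance of green below 1 in 10⁹ under every accrual shape tried; at 95% it is at most 0.6%, and at 98% between 4% and 14%. With the worst-row rule, an amber rating and a recovery strategy are close to certain for a trial on plan. The threshold conflict itself needs no accrual assumption; the probabilities rest on the assumed 99 to 156 people at day 90 and on independence between participants.

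The denominator point is narrower. It concerns the adherence and diary rows only, and red follows from timing alone only if an absolute count of about 63 or more days is required, or 36 days with accrual loaded later than the fitted ramp.

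The consequence is a misleading feasibility rating. Participants, the type I error and the final analysis are not affected. The repeated at-least-100% wording suggests that percentages of a target, as in the recruitment row, were carried over to rows where the target was lost. That origin is an inference; the mismatch is on the page.

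**What to change.** In Table 11:

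1. **Primary-outcome row.** Green at 80% or more, amber from 75% to below 80%, red below 75%, among those who have reached 90 days. The red line should stay. Scaling it as the recruitment row does (75% of 80% = 60%) would accept 0.60 × 690 = 414 evaluable participants against 552 required.
2. **Adherence and diary rows.** Replace the at-least-100% entries with attainable targets agreed with the TSC and funder. The protocol gives no planning value for either; the 80% applies to the primary outcome only and should not be carried over by default.
3. **Denominators of those two rows.** Limit them to participants who have reached 90 days, or state that both are scored on days elapsed.

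The TSC should know that the new amber band is narrow for the numbers available. With 106 participants the standard error at 80% is √(0.8×0.2/106) = 3.9 points, so a result near a boundary should be read with its confidence interval.

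The cost is a wording change agreed with the TSC and funder. It should be made before the month-19 assessment, because thresholds changed after the data are seen carry little weight. Participants, sample size and analysis are unaffected.

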#### 14.4.1. Planned Final Analyses

Final analyses will be performed once the database has been locked.

#### 14.4.2. Planned Subgroup Analyses

Subgroup analyses for the primary outcomes will be performed according to body mass index (BMI < 25 kg/m^2, BMI ≥ 25 to < 30 kg/m^2, BMI ≥ 30 kg/m^2), smoking status (currently smoking, non-smoker), and self-reported categorisation of problem bleeding in previous 90 days (infrequent bleeding (<3 episodes); normal (3– 5 episodes); frequent (>5 episodes); prolonged (≥1 episode(s) lasting ≥14 days)) by including appropriate interaction terms in the regression models. The trial is not powered to detect any interactions hence the subgroup analyses will be treated as exploratory.

#### 14.4.3. Analysis of safety

For safety outcomes, data will be presented descriptively using frequency counts and percentages in each allocated group.

#### 14.4.4. Procedures for missing, unused and spurious data

Every effort will be made to follow up all participants up to the primary endpoint, however, as missing data is inevitable, we will employ statistical techniques for handling missing data for the primary outcomes under the Missing At Random assumption such as further adjustment in the mixed model for variables predictive of missingness. For the primary analysis, only minimisation variables will be adjusted for as covariates and we do not expect any to be missing as they are required for the participant to be allocated.

#### 14.4.5. Analysis sets

For the primary analysis, all randomised participants who receive at least one dose of the trial medication, will be analysed according to allocated treatment group regardless of adherence to the allocated treatment. This will be supplemented by analysing only the participants who would comply with their allocated intervention. Full definition and cut-off for compliance will be specified in the SAP.

For the secondary outcomes, participants will be analysed according to allocated treatment group regardless of adherence to the allocated treatment.

For the safety outcomes, all randomised participants who receive at least one dose of the trial medication will be analysed according to treatment received.

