
Statistical methods
	
For the primary outcome, a two-sided 95% confidence interval for the between-group difference in proportion of people reporting significant improvement will be constructed by fitting a mixed-effect logistic regression model, adjusting for site as a random effect and other minimisation factors as fixed effects. The model will include outcome data from all the 3 timepoints (30, 60, and 90 days) and will include treatment by time interaction to obtain the treatment effect at each timepoint with 90 days as the primary contrast. Non-inferiority of desogestrel will be inferred if the lower bound of this interval lies within the non-inferiority margin of 10%. Analysis will be performed on both the intention to treat (ITT) and per-protocol (PP) population, with ITT being the primary inference. Between-group comparison of secondary outcomes will be based on an appropriate regression model for the outcome, in the generalised linear mixed model framework adjusting for same variables as the primary analysis.

Health Economics
	
Resource Use: The main resources to be monitored include:
 
 
1. The costs associated with treatment (provision of desogestrel and COCP).
 

WPD 3.1\_Protocol Template\_Version 3.1\_20-Apr-2023

[figure not shown]
2. Time and resource use incurred in sexual and reproductive health research (SRH) settings associated with clinical examination, additional treatments and monitoring during the follow up period and to treat any adverse events.
3. Costs associated with discontinuation of the implant.
4. Costs associated with general practitioner (GP) attendances, A&E visits and other National Health Service (NHS) secondary care.
5. Any other health and social care resource use.
6. Costs such as those incurred by implant users and their families (e.g. associated with problem bleeding), will also be captured to allow personal family costs ed as a secondary analysis.

Information on unit costs or prices will be sourced to attach to each resource use item, to enable an overall cost per participant to be calculated (e.g. Unit Costs of Health and Social Care and NHS Reference Costs).

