### 7.11. Assessment of compliance with Treatment

Participants will be asked to complete a daily bleed and medicine adherence diary which will include a question as to whether they have taken their pill. Participants will be prompted (MyCap, email or text message) to complete missing data for 5 days following the scheduled data collection point. Where a participant has multiple episodes of treatment non-compliance on self-reporting, either the NCTU and/or the recruiting site will contact the participant to provide support and to confirm the information is correct and to ascertain the reason for not treatment non-compliance, as well as a welfare check to determine if there are any Serious Adverse Events (SAEs) leading to compliance challenges as per the current trial monitoring plan.

Participants will be asked to return their blister packs to their recruiting clinic at the end of their participation so that self-reported adherence can be confirmed. It is acknowledged that a limitation of this is that participants may have thrown the empty blister packs away.

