#### 8.2.6. IMP dispensing

An IMP pack code, assigned to the correct treatment arm will be linked to the participant at the point of randomisation to allow the recruiting site to dispense the allocated IMP to the participant. Participants will be dispensed their entire 90-day course of IMP at randomisation, in line with the treatment they would receive as part of routine clinical practice.

Participants will be advised to start their treatment **the day after** their clinic visit and randomisation.

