#### 8.2.9. Treatment adherence

Participants will be asked daily (MyCap or paper) if they had taken their pill the previous day at the same time as they are asked about their bleeding status in the previous 24hrs.

Participants will be asked to save all treatment blister packs, for these to be returned to the recruiting clinic and adherence to be reviewed by a member of the clinical team. Participants will be asked to return these to their recruiting clinic during their 3-month standard care review, and where this does not take place the trial research team will facilitate the return of the blister packs.

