### 14.3. Analysis of Outcome Measures

The reporting of the trial will be in accordance with the CONSORT extension to reporting of non-inferiority and equivalence randomised trials [24]. Full details of the statistical analysis will be provided in the Statistical Analysis Plan, which will be finalised and approved by the Trial Steering Committee (TSC) prior to database lock.

Comparative analysis will be performed for the primary outcome on both the intention to treat (ITT) population and some version of the per-protocol (PP) population (preferably complier average causal effect (CACE) analysis, if feasible/identified), as a protection against the ITT's possible increased risk of falsely claiming noninferiority (type I error). Primary estimand will be the treatment policy estimand (i.e., ITT population- analysing data on all randomised participants according to the randomised groups irrespective of subsequent compliance with the treatment allocation) with CACE (or per-protocol) results used to check the consistency. Full definition and cut-off for compliance will be specified in the Statistical Analysis Plan (SAP).

For the primary outcome, a two-sided 95% confidence interval for the between-group difference in proportion of participants reporting significant improvement will be constructed by fitting a mixed-effect logistic regression model, adjusting for site as a random effect and other minimisation factors as fixed effects. The model will include outcome data from all the 3 timepoints (30, 60, and 90 days) and will include treatment by time interaction to obtain the treatment effect at each timepoint with 90 days as the primary contrast. Estimates of model-adjusted difference in proportions and 95% confidence intervals will be obtained by contrasts of average marginal predictions in the fitted model. Non-inferiority of desogestrel will be inferred if the lower bound of this interval lies within the non-inferiority margin of 10%. Missing data for primary outcome will be dealt with through maximum likelihood estimation using mixed-effect model which will use all available follow-up data. Intercurrent events such as discontinuation of assigned treatment or treatment switching, if any, will be dealt with through treatment policy strategy for the primary analysis.

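### Section 14.4.5 limits the primary analysis to participants who received a dose, while section 14.3 and the Trial Summary set it on all randomised participants

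*Protocol*

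**What the plan says.** **Section 14.3** names treatment policy as the primary estimand and explains it as "analysing data on all randomised participants according to the randomised groups irrespective of subsequent compliance with the treatment allocation". Complier average causal effect or per-protocol results are there to check consistency.

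**Trial Summary, statistical methods**, plans both an intention-to-treat and a per-protocol analysis, "with ITT being the primary inference".

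**Section 14.4.5**, for the primary analysis: "all randomised participants who receive at least one dose of the trial medication, will be analysed according to allocated treatment group". The sentence goes on to say that adherence does not matter. For the other outcomes the same section sets no dose condition: "For the secondary outcomes, participants will be analysed according to allocated treatment group regardless of adherence to the allocated treatment". The safety set has the dose condition and is analysed by treatment received. The section defers only the definition and cut-off of compliance to the SAP.

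**How intake is recorded.** Section 8.2.6: "Participants will be dispensed their entire 90-day course of IMP at randomisation". It adds "Participants will be advised to start their treatment" on the day following the visit. Section 8.2.9: "Participants will be asked daily (MyCap or paper) if they had taken their pill the previous day". Sections 7.11, 8.2.9 and 8.3.1 add the return of blister packs to the clinic, with the limitation in 7.11 that "participants may have thrown the empty blister packs away".

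**The concern.** A treatment-policy estimand on all randomised participants includes those who never open the pack. A set that requires one dose leaves them out. These are different populations for the one comparison that decides the trial: a confidence bound set against a 10-point margin. An analysis that follows either section departs from the other, and the protocol does not say which governs.

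The restricted set also needs a fact that the trial cannot establish for everyone. Nobody observes the first pill. It is known from the diary or from a pack that the participant chooses to return. Where both are absent, the protocol gives no rule for deciding whether a dose was received.

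**Working it through.** **1. The statements side by side**

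| Place | Primary population | Dose condition |
|---|---|---|
| Trial Summary | ITT | none |
| 14.3 | all randomised, as allocated | none |
| 14.4.5, primary | randomised, as allocated | at least one dose |
| 14.4.5, secondary | as allocated | none |
| 14.4.5, safety | as treated | at least one dose |

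The primary sentence of 14.4.5 is also at odds with itself. It disregards adherence, yet Table 10 lists zero of 90 pills as one of the adherence categories and classes it as non-adherence. Removing never-starters therefore selects on adherence.

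**2. Can receipt of a dose be established?** Table 8 lets a participant leave the diary and still complete questionnaires. The questionnaire contents listed in 8.2.10 and 8.2.11 include acceptability and side effects but no item on pill-taking. A participant can therefore have a day-90 outcome and no direct record of a dose. Packs may be discarded, and 8.2.7 asks sites to confirm adherence only where possible. That confirmation belongs to the same closing contact at which allocation is revealed, and the order of the two is not stated.

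**3. The plan's sample size.** Inputs from 14.1: 85% in both arms, margin 10 points, one-sided 2.5%, 90% power, Farrington-Manning test.

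- Restricted proportions under a difference of −10 points: 0.787 and 0.887.
- s0 = √(0.787×0.213 + 0.887×0.113) = 0.517; s1 = √(2×0.85×0.15) = 0.505.
- n = (1.960×s0 + 1.282×s1)² / 0.10² = 275.7, so 276 per arm and 552 in total.
- 552 / 0.80 = 690.

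The stated figures reproduce, and power at 276 per arm is 90.0%. There is no arithmetic error here.

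**4. Power in the dosed set.** The protocol gives no never-dosed share q, so q is assumed. The set has 690(1−q) members, of whom 80% have an outcome. Power is Φ[(0.10√n − 1.960 s0)/s1], with n per arm.

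| q | in set | evaluable per arm | power |
|---|---|---|---|
| 0 | 690 | 276.0 | 90.0% |
| 2% | 676 | 270.5 | 89.4% |
| 5% | 656 | 262.2 | 88.5% |
| 10% | 621 | 248.4 | 86.7% |

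**5. Shift in the estimate, equal never-starting.** Assume takers improve at 85% on COCP and 75% on desogestrel, and never-starters improve at the same rate in both arms. The dosed set shows −10.0 points. The all-randomised set shows (1−q)×(−10): −9.8, −9.5 and −9.0 points at q = 2%, 5% and 10%. The shift is 0.2 to 1.0 points.

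**6. Shift in the estimate, unequal never-starting.** Assume takers improve at 85% in both arms, 2% never start in one arm and 5% in the other, and never-starters improve at a rate r. The dosed set shows 0. The all-randomised set shows a difference of size (0.05−0.02)×(0.85−r):

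- r = 20%: 0.03×0.65 = 1.95 points.
- r = 40%: 0.03×0.45 = 1.35 points.

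For scale, the unadjusted 95% half-width at 276 per arm is 1.960×√(0.255/276) = 6.0 points.

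Steps 5 and 6 treat every never-starter as having an outcome. Those with no questionnaire at any time point add no outcome information under either definition, so the real shift would be smaller.

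**The case against.** **Stronger readings that the text does not support**

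- A reader might infer that intake is known only by self-report and cannot be verified. Sections 7.11, 8.2.9 and 8.3.1 plan pack return to confirm adherence, with help in returning packs where there is no clinic visit, and 8.2.7 asks the site to confirm adherence. An untouched returned pack shows that no dose was taken. The check is incomplete, not absent.
- A reader might infer that anyone with a blank diary and no pack would be dropped. No section says so. The rule is simply not stated, and the SAP, which was not available here, may contain one.
- A reader might infer that the analysis population could be picked once results are known. Under 14.3 the SAP is finalised and approved by the Trial Steering Committee before database lock, and Table 4 keeps the trial statisticians blind until after the first lock. The ambiguity is real, but the protocol does not permit a results-driven choice.

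**The case that little is at stake.** Participants and site staff are blinded, so the decision to start should rarely depend on allocation. Someone with early side effects of the drug has taken a dose, and one positive diary entry shows it. Diary prompts and a five-day window for late entries make a wholly blank record less likely. If desogestrel is truly worse, the dosed set is slightly the more conservative one (step 5).

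**What stands.** These arguments limit the size of the effect; none reconciles the two definitions. Section 14.3 already gives the protection against diluted differences to the complier or per-protocol analysis, so the primary set need not supply it. Nor is this a matter left to the SAP, because 14.4.5 defers only the compliance definition and states the primary set itself.

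**Conclusion.** The contradiction is real and concerns the primary population. Sections 14.3 and 14.4.5 cannot both be followed, and the dose condition is a post-randomisation exclusion that the declared estimand does not allow. Receipt of a dose is not reliably verifiable for every participant, so the restricted set could not be formed cleanly even if it were wanted.

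The likely numerical effect is small. It is 0.2 to 1.0 points under equal never-starting of 2% to 10% with a 10-point true difference among takers. It is about 1.4 to 2.0 points only with 2% against 5% never starting and never-starters improving at 20% to 40%. All of these shares and rates are assumptions; the protocol gives none. The larger shift could matter for a borderline result against a 10-point margin, but blinding makes such an imbalance unlikely. This should be fixed; it does not threaten the trial's validity as designed.

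**What to change.** In the primary-analysis sentence of 14.4.5, delete the clause that requires at least one dose. It would then say, for example: *For the primary analysis, every randomised participant is analysed in the allocated group, whether or not trial medication was taken.* This matches 14.3 and the Trial Summary. Keep the dose condition for the safety set only.

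If a dosed set is wanted as a sensitivity analysis, label it as such and state how receipt of a dose is decided when the diary is blank and no pack is returned.

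The cost is one sentence in the protocol, and the same change in the SAP if it repeats the dose condition, which could not be checked. The sample size stays at 690 and the planned power at 90%. No trial procedure changes.
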